In a recently published in vitro study from Australia, the efficacy of ivermectin used as an antiparasitic agent on SARS-CoV-2 was evaluated and Vero/hSLAM cells were infected with this virus in vitro and exposed to ivermectin, after 48 hours there was a 99.8% reduction in viral load. Based on these studies, it can be thought that ivermectin, which has also been shown to have antiviral efficacy in different studies, may also be effective in COVID19 patients (8).

In this study, it is aimed to evaluate the effect of ivermectin addition to the "Hydroxychloroquine ± Favipiravir ± Azithromycin" combination therapy, which is the reference treatment recommended in the "Covid19 Guideline" prepared by the Ministry of Health, on clinical response in patients with severe COVID19 pneumonia and to investigate the safety of ivermectin use in these patients (10).

Material and Method

The study will be conducted as a prospective, randomized, controlled, single-blind Phase 3 study. Patients with severe COVID19 disease who were hospitalized in Afyonkarahisar Health Sciences University, Health Sciences University Istanbul Sultan Abdülhamid Han Training and Research Hospital, Ankara City Hospital and Health Sciences University Ankara Gülhane Training and Research Hospital COVID19 service and intensive care units will be included in the study.

There will be two patient groups in the study, the study arm and the control arm. A total of 60 patients, including 30 in both arms, are planned to be included in the study.

Patient Selection and Inclusion Criteria

Patients who were hospitalized with a pre-diagnosis of *severe COVID-19 pneumonia and thereafter diagnosis of COVID-19 was also confirmed microbiologically with PCR positivity in respiratory tract samples were included into the study (13). They were randomized to the study and control group, respectively.

- * Patients with at least one of the criteria below were accepted as patients with severe COVID-19 pneumonia;
- a. Presence of tachypnea ≥30/minute, SpO2 level <90% in room air, PaO2/FiO2 <300 in oxygen receiving patient
- b. Presence of specific radiological finding for Covid-19 in lung tomography (bilateral lobular, peripherally located, diffuse patchy ground glass opacities)
- c. Mechanical ventilation requirement
- d. Acute organ dysfunction findings; patients with SOFA (sepsis-related organ failure assessment) score> 2

THE SEQUENTIAL ORGAN FAILURE ASSESSMENT (SOFA) SCORE

0	1	2	3	4

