Ivermectin antiparasitically as a single daily or multi-dose intermittent sequential; In dengue fever infection, considering the use of 200 or 400 mcg / kg / day as an antiviral for 3 days, it is seen that the total dose given in antiviral treatment reaches up to 1200 mcg / kg / day (14,15,16). Based on all these studies, we planned to use ivermectin at a dose of 200 mcg / kg / day, which is approved by the FDA, in our study. Definitive recommendations for treating COVID19 disease Although not, the duration of treatment with antiviral drugs is recommended as 5 days in the guide prepared by the Scientific Committee of the Ministry of Health. Considering that the average duration of symptoms in patients is 5-7, the duration of ivermectin treatment was planned as 5 days in our study, and it was planned to reach a total dose of 1000 mcg / kg / day, close to the total dose used in viral infections in the literature. The treatment can be terminated in less than 5 days if the patients reach the treatment early or if there are side or toxic effects.

Study Design

In all patients included in the study; demographic data, comorbid conditions, admission symptoms, complete blood count and biochemical blood examinations at the time of admission, initial SARSCoV-2 PCR results and thoracic tomography findings at presentation will be recorded.

During the study; respiratory findings and laboratory parameters of the patients will be recorded on the 1st, 3rd and 5th days of the treatment and on the 1st, 3rd and 5th days after the treatment, during the follow-up period. Side effects observed during the treatment in all patients also will be recorded.

Primary and secondary endpoints for efficacy and safety assessment in the study will be determined as follows:

Primary endpoint: Clinical responses and drug side effects obtained in patients on the 5th day, at the end of the ivermectin treatment will be evaluated. Extubation in mechanically ventilated patients, respiratory rate <26, SpO2 level in room air > 90%, PaO2 / FiO2> 300 in patients receiving oxygen, presence of at least two of the 2-point reduction criteria in SOFA score will be evaluated as "*clinical response*".

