Date: 04.05.2020 Version: 3

STATISTICAL ANALYSIS PLAN

Study name: Evaluation Of The Effectiveness And Safety Of Adding Ivermectin to

Treatment in Severe COVID-19 Patients

Study protocol cod: IVMC_03

Ethics committee approval number and date: 139/03.04.2020

Coordinator researcher: [name]. [name]

STATISTICAL ANALYSIS PLAN

Convenience Sampling method will be used in the study. Unilateral blinding will be made in determining which of the study and control groups participating patients will be included in the study, those with an odd number will be included in the study group, and those with an even number will be included in the control group.

In determining the sample size, it was planned to include 30 individuals in each group based on the number of available kits. In this case, the values of 0.05 for Type I Error Rate, 0.67 for Effect Size and 0.80 for Power were reached.

The Chi-Square test will be used in the evaluation of categorical data, the Wilcoxon test for in-group comparisons, and the Mann-Whitney U test for intergroup comparisons. For statistical significance, the value of p=0.05 will be taken into account and the analyzes will be carried out in the SPSS 20.0 package program.

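### The primary day-5 response rule does not restrict the respiratory-rate item to unventilated patients or count new ventilation as non-response, so a newly ventilated patient can score as a responder

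*Protocol*

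**What the plan says.** Protocol, Study Design, primary endpoint: response is assessed on day 5, at the end of ivermectin treatment. Four items are listed first: "Extubation in mechanically ventilated patients, respiratory rate <26, SpO2 level in room air > 90%, PaO2 / FiO2> 300 in patients receiving oxygen". The sentence then runs on: "presence of at least two of the 2-point reduction criteria in SOFA score will be evaluated as" clinical response. Taken literally, the last part is garbled, because it attaches the count to SOFA alone. The secondary endpoint, in the next paragraph, says plainly that at least two of its listed criteria are needed. The natural reading of the primary endpoint is therefore at least two of five items, the fifth being a 2-point fall in SOFA.

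Protocol, Patient Selection and Inclusion Criteria: any one severity criterion is enough for entry, and one of them is "c. Mechanical ventilation requirement". The trial will therefore enrol both ventilated and unventilated patients.

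Neither document says how respiratory rate is scored in a ventilated patient, whether the extubation item refers to ventilation at entry or on day 5, or how a patient who becomes ventilated during treatment is classified.

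**The concern.** Starting invasive ventilation is a worsening that a response endpoint in severe COVID-19 pneumonia should recognise. Under this rule a newly ventilated patient can still collect two items. On a ventilator the recorded rate may reflect the machine setting and not the disease, so the rate item can be met without clinical improvement; the patient then needs only one more item.

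The direction of the error depends on which arm has more ventilated patients. If ivermectin prevented ventilation, controls would gain more such responders and the observed benefit would shrink. If ivermectin increased ventilation, the ivermectin arm would gain them and the observed harm would shrink. The study is small and described as single-blind, with no placebo mentioned, so leaving the scoring to be settled at analysis also leaves room for judgement made with knowledge of the arm.

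**Working it through.** **1. The plan's own figure.** The SAP says that "it was planned to include 30 individuals in each group based on the number of available kits", and that with this number "the values of 0.05 for Type I Error Rate, 0.67 for Effect Size and 0.80 for Power were reached". With n = 30 per arm, effect size 0.67 and alpha 0.05, a one-sided Mann-Whitney test (relative efficiency 3/π) gives power 0.805, which reproduces 0.80. Two-sided versions of the z, t and rank tests give 0.66-0.74. The SAP does not state sidedness or the effect-size metric, and it assumes no response rates. The figure therefore neither supports nor weakens this point; only the 30 per arm is used below.

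**2. Scoring a patient on invasive ventilation on day 5.**

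| Item | Can it be met? |
|---|---|
| Extubation | No |
| Respiratory rate <26 | Yes; no restriction in the text |
| SpO2 >90% in room air | No; not on room air |
| PaO2/FiO2 >300 if receiving oxygen | Yes |
| SOFA fall of 2 points | Yes |

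Three items remain open and two are needed.
- Rate below 26: responder in 3 of the 4 patterns of the other two items (either or both met).
- Rate not below 26: responder in 1 of 4 (both met).
- Rate alone: never a responder.

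These are counts of patterns, not probabilities.

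**3. A worked case.** Suppose a patient is on mask oxygen at entry and is intubated on day 3. On day 5 the recorded rate is 18 and PaO2/FiO2 is 310. Extubation no, rate yes, room-air SpO2 no, PaO2/FiO2 yes, SOFA not needed. The count is 2, so the patient is a responder.

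The SOFA route is narrower for such patients. In the protocol's SOFA table, respiratory scores 3 and 4 require respiratory support. A patient without support at entry scores at most 2 on that component, and a 2-point fall from it alone would need PaO2/FiO2 of at least 400. Otherwise the fall must come from other organs, or from a patient whose non-invasive support at entry already counted.

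**4. Size.** One patient in 30 is 1/30 = 3.3 percentage points of an arm's response rate. The documents give no ventilation rates, so the following are assumptions: 10-30% of controls and 10% of ivermectin patients newly ventilated on day 5; all with a recorded rate below 26; a proportion q of 20-40% of them meeting a further item.

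Shrinkage of the difference = q × (control ventilation − ivermectin ventilation).

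| Controls | Ivermectin | q = 0.20 | q = 0.40 |
|---|---|---|---|
| 10% | 10% | 0 points | 0 points |
| 15% | 10% | 1 point | 2 points |
| 30% | 10% | 6 − 2 = 4 points | 12 − 4 = 8 points |

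In patients, the largest case is a net 30 × 0.08 = 2.4 and the 4-point case is 30 × 0.04 = 1.2.

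**5. What that does to power.** Power = Φ[(d − 1.96·SE0)/SE1], with SE0 = √[p̄(1−p̄)·2/30] and SE1 = √[p1(1−p1)/30 + p2(1−p2)/30]. Take an assumed true response of 40% vs 72%:
- No misclassification: d = 0.32, SE0 = 0.128, SE1 = 0.121, power 0.72.
- 4-point shrinkage (46% vs 74%): power 0.60.
- 8-point shrinkage (52% vs 76%): power 0.49.

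**The case against.** The strongest reply is that the sentence can be read to block the problem. Two items are tied to a support group, so extubation could be meant as the requirement for anyone on a ventilator. That reading is possible, but the text lists extubation in parallel with the other items under one count and does not make it compulsory. If the sponsor intends it, it has to be written down. This keeps confidence in the point moderate.

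Several stronger readings are tempting, and the documents do not support them:

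- **That ventilated patients receive the rate item automatically.** No ventilator settings or modes are given. A rate below 26 is plausible when the machine sets it, but it is an inference, and a second item is always needed.
- **That becoming intubated leaves the score untouched.** It removes the room-air SpO2 item and opens respiratory SOFA scores 3 and 4, which makes a 2-point fall harder.
- **That a patient ventilated at entry whose PaO2/FiO2 rises from 90 to 210 shows worsening being rewarded.** That patient improved: the respiratory SOFA score goes from 4 to 2. Whether improvement while still intubated should count is a choice of endpoint.
- **That the treatment difference is known to shrink by 4-8 points.** That follows only from a 30% vs 10% split. With equal ventilation the shrinkage is zero, and if newly ventilated patients met a further item only 5% of the time, the same split gives 0.05 × 20 = 1 point.
- **That harm would be hidden.** Mortality, SpO2 and PaO2/FiO2 changes are compared separately, and oxygen and intensive-care need are items of the secondary endpoint. Harm could still be seen there, although this does not repair the primary endpoint.

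**Conclusion.** The point holds in a limited form. On the most natural reading, the primary response rule can classify a patient newly on invasive ventilation on day 5 as a responder. This is more than missing detail, because applying the rule as written gives the wrong answer for such a patient. It requires a recorded rate below 26 plus PaO2/FiO2 above 300 or a 2-point SOFA fall, or both of those without the rate.

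How often this would happen cannot be estimated from the documents. The 0-8 point range rests wholly on the assumed ventilation and item rates. Its upper end also treats every patient ventilated on day 5 as newly ventilated, so it should be read as an illustration and not as an expected bias. With 30 per arm, even one or two such patients are not negligible.

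**What to change.** Amend the primary endpoint before analysis, with the same rules in both arms:

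1. State that clinical response on day 5 means at least two of the five listed items.
2. Count the respiratory-rate item only in patients not on invasive mechanical ventilation on day 5.
3. Classify any patient not on invasive mechanical ventilation at entry who is on it on day 5 as a non-responder.

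Use the term invasive mechanical ventilation throughout, so that non-invasive support is not left in doubt. A patient ventilated at entry and still intubated could then respond only with both PaO2/FiO2 above 300 and a 2-point SOFA fall; the sponsor should confirm that this is intended. These rules do not settle death before day 5, which the current text also leaves unclassified.

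The cost is three sentences. Respiratory findings are already recorded on days 1, 3 and 5, and the extubation item already needs ventilation status. The change affects scoring only, not care. The downside is a slightly lower reported response rate.

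### Patients admitted on CT findings or non-respiratory SOFA points can meet the primary response before dosing, and the SAP neither counts them by arm nor adjusts for day-1 status

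*Protocol*

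**What the plan says.** **Entry.** Protocol, Patient Selection and Inclusion Criteria: "Patients with at least one of the criteria below were accepted as patients with severe COVID-19 pneumonia". Criterion (a) is respiratory: "Presence of tachypnea ≥30/minute, SpO2 level <90% in room air, PaO2/FiO2 <300 in oxygen receiving patient". Criterion (b) is radiological: "Presence of specific radiological finding for Covid-19 in lung tomography". Criterion (c) is a need for mechanical ventilation. Criterion (d) is organ dysfunction: "patients with SOFA (sepsis-related organ failure assessment) score> 2". Material and Method states the setting: "COVID19 service and intensive care units will be included in the study", so ward patients are eligible.

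**Primary response.** Protocol, Study Design, assesses it on day 5. The items are extubation, then "respiratory rate <26, SpO2 level in room air > 90%, PaO2 / FiO2> 300 in patients receiving oxygen, presence of at least two", and the sentence runs on: "presence of at least two of the 2-point reduction criteria in SOFA score will be evaluated as" a clinical response. Nothing requires an item to have been unmet at the start.

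**Secondary response.** The next paragraph, five days after treatment ends, asks plainly for any two of its listed items. These include not needing oxygen and not needing intensive care.

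**Baseline data.** Study Design: "respiratory findings and laboratory parameters of the patients will be recorded on the 1st, 3rd and 5th days of the treatment". Whether day 1 means before the first dose is not stated.

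**Analysis.** The SAP gives chi-square for categorical data, Wilcoxon within groups and Mann-Whitney between groups. It has no stratum, covariate, count of day-1 status by arm or supporting analysis. Allocation is by odd or even number, with 30 per group.

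**The concern.** A day-5 status endpoint can be legitimate, since staying above a threshold may itself be a benefit. The difficulty is that entry and response are not aligned. Every response item has a counterpart in entry criterion (a), (c) or (d), but the CT criterion has none, and criterion (d) can be met with points from non-respiratory organs. Some patients may therefore start treatment already classed as responders, and remain so if unchanged or somewhat worse.

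Such patients add responders to both arms. If they are balanced, the arm difference shrinks and power is lost, without bias. If chance puts more of them in one arm, an unadjusted comparison can show an effect that is not there or hide one that is. With 30 per arm, both are possible unless these patients are few.

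**Working it through.** **1. Can it happen?** Take a patient admitted on (b) alone, with criterion (a) read as any one of its signs. Not meeting (a) means a rate below 30 and room-air SpO2 not below 90%. Response needs a rate below 26 and SpO2 above 90%. A rate of 20 with SpO2 94% meets both on day 1. The same holds for a (d) entrant whose SOFA points are non-respiratory. For the secondary endpoint, a ward patient not on oxygen meets two items at entry.

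**2. The plan's own figure.** The SAP states power 0.80 for effect size 0.67, alpha 0.05 and 30 per group, without response rates or sidedness. Read as a standardised mean difference, this reproduces only as a one-sided Mann-Whitney test (0.805); two-sided it is 0.70, or 0.72 by t test. Read as Cohen's h for two proportions, it gives 0.73 two-sided and 0.83 one-sided. The SAP therefore supplies no response rates to work from, and those below are assumptions.

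**3. Model.** Let f be the share already meeting two items, r the proportion of them still responders on day 5, and q the response rate in the rest. The arm's rate is p = f·r + (1 − f)·q. At f = 0.30 and r = 1:
- control 0.30 + 0.70 × 0.30 = 0.51
- study 0.30 + 0.70 × 0.65 = 0.755
- difference 24.5 points, which is 0.70 × 35

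Chi-square power is exact (uncorrected Pearson, two-sided 5%). CMH is simulated, with the number already qualifying drawn as binomial(30, f) in each arm: z = Σ(x − n₁m/N) / √Σ[n₁n₂m(N − m) / (N²(N − 1))], summed over the two day-1 strata. In each stratum x is study-arm responders, m all responders, n₁ and n₂ the arm sizes, and N their sum.

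**4. Power, 30% vs 65% in the rest** (chi-square at f = 0: 0.80). Cells are chi-square → CMH.

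| Already-qualifying patients still responding | f = 20% | f = 30% | f = 40% |
|---|---|---|---|
| 100% in both arms | 0.60 → 0.69 | 0.50 → 0.63 | 0.42 → 0.56 |
| 90% in both arms | 0.60 → 0.65 | 0.49 → 0.57 | 0.39 → 0.47 |
| 80% in both arms | 0.60 → 0.63 | 0.49 → 0.53 | 0.38 → 0.42 |
| 80% control, 95% study | 0.69 → 0.74 | 0.64 → 0.71 | 0.59 → 0.67 |

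- At f = 5% the gain is 2 points or less. At f = 10% chi-square is 0.71 and CMH 0.75, 0.73 and 0.72 for 100%, 90% and 80% retention.
- With 45% vs 80% in the rest, gains are 5–9, 3–4 and 1–2 points for the same three retentions.
- If day-1 status does not predict response, CMH costs about 1 point (0.79 against 0.80).

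**5. Chance imbalance.** Averaged over all allocations, chi-square holds its level (0.047–0.052). The probability that the arms differ by 6 or more such patients is 0.018, 0.075, 0.12 and 0.147 at f = 10, 20, 30 and 40%. Take 12 vs 6, no drug effect, 30% response in the rest and all already-qualifying patients remaining responders:
- expected responders are 12 + 18 × 0.30 = 17.4 and 6 + 24 × 0.30 = 13.2, or 58% vs 44%
- chi-square rejects with probability 0.13 and CMH about 0.05; with 80% retention, 0.095 and 0.05
- at 11 vs 7, chi-square rejects with probability only 0.056

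Under the 30% vs 65% effect (100% retention, then 80%):
- 12 in control, 6 in study: chi-square power 0.15 or 0.28; CMH 0.62 or 0.53
- imbalance reversed: chi-square 0.84 or 0.70; CMH 0.64 or 0.53

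**The case against.** The strongest points against are these.

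- **It rests on readings and an unknown.** Literally, the sentence attaches the two-item rule to the SOFA reduction. But there is only one SOFA item, so that reading makes no sense, and the secondary endpoint's wording supports any two items. That f is unknown stands: the finding is that this can happen, not how often.
- **The starting power is not the SAP's.** 30% vs 65% is h = 0.716, not 0.67. If 0.67 already describes all enrolled patients, nothing is lost against plan. This stands. The safer measure is CMH against chi-square on the same data.
- **The large gains need every such patient to remain a responder.** This also stands; nothing in the documents favours 100% retention over 80%.
- **The 12 vs 6 case is selected.** A gap of 6 or more in a given direction has probability 0.06 at f = 30%. At 10 vs 8, with 30% response in the rest and all staying, chi-square is conservative (0.020). Imbalance in any prognostic factor does similar harm. All true, but this factor is built into the endpoint's own definition.
- **A continuity correction reverses the benefit.** With full retention, corrected CMH gives 0.58/0.50/0.42, no gain. At 80% retention it falls to 0.52 at f = 20% and 0.31 at f = 40%, below plain chi-square. The uncorrected version must therefore be named.
- **Changes in SpO2 and PaO2/FiO2 are already compared between arms.** They are, but separately from the binary response, which they do not repair.

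**Conclusion.** The point holds. On the only sensible reading of the endpoint sentence, patients admitted on CT findings or non-respiratory SOFA points can be primary responders before treatment, and the SAP does not say how day-1 status is handled. The secondary endpoint has the same feature.

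The size depends on f and on how many of these patients keep their status; the documents give neither. Over f = 20–40% with 30% vs 65% in the rest, stratifying gains 3 to 14 points of power. It gains almost nothing if f is near 5% and costs about 1 point if day-1 status is not prognostic. There is no average inflation of type I error; the false-positive risk is conditional on a marked chance imbalance. This is a low-cost improvement to the analysis. It does not show that the planned test is invalid.

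**What to change.** 1. Rewrite the primary endpoint sentence so that the two-item rule clearly refers to the listed items. State which items apply to which patients: extubation, PaO2/FiO2, and how room-air SpO2 is scored in a patient on oxygen.
2. Keep all patients. For the primary response, replace the plain chi-square with a CMH test **without continuity correction**, stratified by whether the patient already met at least two items before dosing. Confirm that the SAP's named software reports that version.
3. Report the number already meeting two items by arm. Pre-specify the comparison in the remaining patients as supporting. It has power 0.70/0.64/0.57 at f = 20/30/40%: essentially the same test as CMH at full retention and stronger at equal 80–90% retention. It is weaker than CMH (0.74/0.71/0.67) if the drug helps patients hold their status (80% vs 95%). It answers a narrower question, so it should not be primary.
4. Treat the secondary endpoint likewise, with its own items. Baseline need for intensive care must then be recorded, which the protocol does not explicitly list.

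Requiring items to be newly met is not recommended. A CT-only entrant on room air with SOFA 0–1 would have no item left to meet. If all already-qualifying patients counted as non-responders, power would be 0.61/0.52/0.44, little better than now.

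**Cost:** endpoint and SAP wording, one table row and one stratified test, with no extra patients. The primary stratum uses respiratory findings already due on day 1, but they must be taken before the first dose, at the same point in both arms.

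**Limits:** stratifying recovers only part of the power and handles only this factor. A patient who worsens but stays past two thresholds still counts as a responder, and the odd/even allocation is not cured.
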